3.4.3 Time to Event Variables

Survival analysis techniques will be used to analyze the time-to-event variables that occur at or after 30 days of follow-up. All of these analyses will be performed with time defined from date of randomization and from date of procedure. Subjects without events will be censored at their last known event-free time point. If this event-free time point occurs after the analysis time point, the days to event variable will be set equal to the analysis time point so that the patient will be included in the analysis (e.g. if the last data point was collected at 3 years and 1 week post randomization, for the 3 year analysis, this patient is censored at exactly 3 years [1095 days]). For patients who did not have an event or early withdrawal and have not yet completed the 3 year visit, they will be censored at the time of their last follow-up. Time to first event curves will be constructed using Kaplan-Meier estimates.

For time to event variables such as MI, stroke and and revascularization, at all post discharge results will be summarized with Kaplan-Meier estimates of event rates. For time to event variables such as death and composite endpoints including death, deaths will be included for patients who dropped out early, but had a known death date, prior to study day 1095, from the national death registry.

For time to event analyses, hazard ratios, confidence interval for the hazard ratios, and p-values may also be presented from a Cox proportional hazards model.

Formulas are given below. Please note that in using these formulas, it is assumed that the data are independent observations.

The Kaplan-Meier product-limit estimator is defined as follows:

$$\hat{S}(T) = \begin{cases} 1 & \text{if } T_{\min} > T \\ \prod_{A \le T_i \le T} \left[1 - \frac{d_i}{r_i} \right] & \text{if } T_{\min} \le T. \end{cases}$$

The variance of S(T) is estimated by Greenwood's formula where

$$\hat{V}\left[\hat{S}(T)\right] = \hat{S}(T)^2 \sum_{A \le Ti \le T} \frac{d_i}{r_i(r_i - d_i)}$$

The Kaplan-Meier failure rate estimator and it's variance are defined as

$$\hat{F}(T) = 1 - \hat{S}(T)$$
$$\hat{V}[\hat{F}(T)] = \hat{V}[\hat{S}(T)]$$

 $100(1-\alpha)$ % Confidence Interval for the hazard ratio

Cox proportional hazards regression will be used to obtain the confidence interval for the hazard ratio. The phreg procedure in SAS will be used to obtain the Wald confidence limits. An example of the code is as follows:

ods output ParameterEstimates=*Out1*; proc phreg data=*InFile*; model *TimeVar*Eventvar* (0)= *Group* / rl; run;

3.4.4 Hypothesis Testing

Formal non-inferiority and superiority tests are planned for the primary and powered secondary endpoints. These endpoints are Kaplan-Meier failure rate estimates (higher rate is worse).

All non-inferiority tests will be one-sided. The null and alternative hypotheses will be of the following form (assuming showing A non-inferior to B):

 $\begin{array}{ll} H_0: \ Endpoint_A - Endpoint_B \geq \Delta \\ H_A: \ Endpoint_A - Endpoint_B < \Delta \end{array}$

For one-sided superiority test, the null and alternative hypotheses will be of the form (assuming showing A superior to B):

H₀: Endpoint $_{\rm A}$ – Endpoint $_{\rm B} \ge 0$ H_A: Endpoint $_{\rm A}$ – Endpoint $_{\rm B} < 0$

For two-sided superiority test, the null and alternative hypotheses will be of the form

H₀: Endpoint $_A$ – Endpoint $_B$ = 0 H_A: Endpoint $_A$ – Endpoint $_B \neq 0$

Methods for testing are as follows. Detailed specifications on non-inferiority deltas, significance levels, and decision rules are provided in the section on analysis of endpoints.

1. Test for non-inferiority

The test for non-inferiority will be based on the one-sided $(1-\alpha)$ confidence interval of the difference between the two treatment arms. If the upper bound of the one-sided $(1-\alpha)$ confidence interval is less than Δ , then it will be concluded that the null hypothesis can be rejected and non-inferiority will be declared.

2. Test for superiority

For one-sided superiority test, if the one-sided $(1-\alpha)$ confidence interval is less than 0, then it will be concluded that the null hypothesis can be rejected and superiority will be declared.

For two-sided superiority test, if the $(1-\alpha)$ confidence interval does not contain 0, then it will be concluded that the null hypothesis can be rejected and superiority will be declared.

Caution must be exercised when interpreting p-values displayed for analyses other than those performed for the primary and powered secondary endpoints, as the study was not powered to detect differences for any of those other variables. The resulting p-values, whether or not less-than 0.05, may be a result simply due to pure chance.

3.5 SUBGROUPS FOR ANALYSIS

The primary and major powered secondary endpoints will be analyzed by the following subgroups. The treatment comparisons in these analyses are not powered for hypothesis testing and are descriptive in nature. Data described below will be summarized as seen in the table mockups.

For each covariate, two models will be will be run:

- one with just treatment and the covariate. It will be testing if there is a significant effect regardless of the the covariate. The 3 year Kaplan-Meier estimates for each treatment along with the percent difference and 95% confidence interval of the differences will be presented, as well as hazard ratios and 95% confidence intervals of the hazard ratios. Forest plots will be presented, including results for all subgroups analyzed
- a second model, containing also the interaction term of covariate and treatment, will be testing if the treatment effect varies significantly with the covariate values. For any statistically significant interaction terms a Kaplan-Meier plot will be displayed by subgroup.

Subgroup details are as follows.

Diabetic subgroups:

• Diabetes mellitus requiring medication, defined as subjects treated with oral hypoglycemic medications or insulin vs. non treated or no diabetes

Age:

- $Age \ge Median, Age < Median$
- Age \geq 75, Age < 75

Gender: male vs female

Other baseline characteristics:

- Body mass index; \geq Median, < Median
- Prior MI: yes vs. no
- $LVEF \ge$ Median, LVEF < Median
- $LVEF > 40\%, LVEF \le 40\%$
- Chronic kidney disease (CKD): Creatinine Clearance (ml/min) from Cockcroft-Gault formula: [(140-age)(weight in kg)]/(72 x Serum creatinine in ml/min) (*0.85 in women)
 CKD< or ≥ 60ml/min
- Geographic location (US vs. EU vs. Other); US vs other; NA vs. EU vs other; NA vs. other

Disease characteristics:

- Number of diseased vessels $\geq 3, <3; \geq 2, <2$ (core lab)
- **Distal Left Main Bifurcation Involvement** (yes/no) (core lab)
- Chronic Total Occlusion of non left main (yes/no) from angiography (core lab)

Scores at baseline:

- SYNTAX score:
 - \circ by core lab \geq Median, < Median; and by tertiles
 - by core lab \geq 23, < 23
 - by core lab \geq 33, < 33
 - \circ clinical SYNTAX score \geq Median, < Median
 - o clinical SYNTAX score $\geq 23, < 23$
 - o clinical SYNTAX score \geq 33, < 33

- Syntax Score II (SSII); developed by Farooq et al.⁷ \geq Median, < Median; and by tertiles
- ACEF score = age (years)/ejection fraction (%) (+1 if serum creatinine value is >2 mg/dL), then categorized as < or ≥ median

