Moreover, as described above, the SYNTAX trial had few exclusion criteria, and post hoc analyses using the SYNTAX score have demonstrated a clear advantage of CABG for those subjects with the highest risk SYNTAX tertile (score \geq 33). In contrast, for subjects randomized to PES vs. CABG with a SYNTAX score of \leq 32 (approximately two thirds of the left main cohort), mortality was lower with PCI at 3 years, and a trend was present for reduced composite death, MI or stroke with PCI, with nonsignificantly different rates of unplanned revascularization between PCI and CABG. However, as a post hoc, subgroup analysis, these findings must be considered hypothesis-generating, warranting testing in an appropriately powered randomized trial. Furthermore, the primary endpoint of SYNTAX was measured at one year, a period which may be too early to capture the intermediate term outcomes between PCI and CABG.

In addition, as described below, the XIENCE V stent has been shown to be superior to the PES, with lower rates of stent thrombosis, MI and target lesion revascularization demonstrated in four randomized trials (SPIRIT II, SPIRIT III, SPIRIT IV and COMPARE). Use of XIENCE V may therefore further improve outcomes in the PCI arm. Since the SYNTAX trial was conducted, improvements in PCI technique and adjunct pharmacotherapy have occurred (e.g. strategies to manage the bifurcation, use of intravascular ultrasound and fractional flow reserve, bivalirudin and optimal thienopyridine use), as well as improvements in CABG (optimal use of arterial conduits, screening for and management of peri-procedural stroke risk, e.g., with epi-aortic ultrasound, and optimal use of pre-, intra-, and post-procedural pharmacotherapy).

Thus, an appropriate trial to evaluate PCI vs. CABG in subjects with disease of the left main stem is justified, and would:

- be restricted to those patients in whom clinical equipoise is present between PCI and CABG (SYNTAX score ≤32);
- utilize optimal interventional and surgical techniques (allowing for acceptable variation between centers);
- be adequately powered for a primary endpoint of mortality, MI or stroke, and at a later endpoint than one year (e.g. at 3 years); and

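### SAP 3.5 lists its continuous covariates only as cuts; one pre-specified continuous interaction test per score would use the data better, although these analyses are declared unpowered and descriptive

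*SAP*

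**What the plan says.** SAP 3.5 applies to the primary and both powered secondary endpoints. For each covariate it fits a model with treatment and the covariate, then a second model "containing also the interaction term of covariate and treatment, will be testing if the treatment effect varies significantly with the covariate values". Hazard ratios are reported, with a forest plot of all subgroups. A further display depends on the test: "For any statistically significant interaction terms a Kaplan-Meier plot will be displayed by subgroup".

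The continuous or many-valued covariates are listed in these forms:

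- Age: median; 75.
- BMI: median.
- LVEF: median ("Median, LVEF < Median"); 40%.
- Creatinine clearance: "CKD< or ≥ 60ml/min".
- Core-lab SYNTAX: "Median, < Median; and by tertiles"; also 23 and 33.
- Clinical SYNTAX: median; 23; 33.
- SYNTAX II: median; tertiles.
- ACEF: computed as a number, "then categorized as < or ≥ median".

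That is 2 + 1 + 2 + 1 + 4 + 3 + 2 + 1 = 16 versions of eight scores. The same section sets their status: "The treatment comparisons in these analyses are not powered for hypothesis testing and are descriptive in nature". Protocol 9.1.4 and 21.2 also call subgroup analyses exploratory.

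The only instruction to enter continuous data as continuous is in SAP 3.6.1.3, the covariate-adjusted model. That model lists no interaction with treatment and enters SYNTAX as two dummy variables.

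**The concern.** The stated aim is to learn whether the treatment effect changes with the value of the covariate. A two-group cut asks something coarser: whether the average effect differs between two halves or between a tail and the rest. All patients on one side of the cut are treated as alike, although the trial holds their actual values.

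This matters most for anatomical complexity. Protocol 2.6 builds the case for the trial partly on SYNTAX score: "post hoc analyses using the SYNTAX score have demonstrated a clear advantage of CABG for those subjects with the highest risk SYNTAX tertile". It calls that observation hypothesis-generating and in need of testing. Readers will look to the forest plot for any remaining variation within the enrolled range. Core-lab SYNTAX alone would carry four correlated interaction p-values for one question, and the SAP does not say which one counts.

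At stake is how informative an exploratory result is. No confirmatory conclusion is involved.

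**Working it through.** **1. Anchor to the plan's own figure.** The documents give no power for any interaction test, so the design figure is the check. Inputs from SAP 2.5.1: 11% per arm at 3 years, margin 4.2%, one-sided alpha 0.025, 80% power, 8% lost.

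n per arm = (1.960 + 0.842)² × 2 × 0.11 × 0.89 / 0.042² ≈ 872. Dividing by 0.92 gives 948 per arm, or 1,896 in total. The SAP says 1,900, so the figure reproduces. With 950 × 0.92 = 874 per arm, power is 80.1%.

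**2. Information kept by a cut.** Assume a normal covariate and an interaction linear in it. A cut leaving a share p in one group keeps φ(z_p)² / [p(1 − p)] of the information; at the median this is 2/π. The cut version then has power Φ[(1.960 + z_power) × √kept − 1.960]. From a continuous test with 80% power:

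| Form | Information kept | Power left |
|---|---|---|
| Median split | 63.7% | 60.8% |
| 25/75 cut | 53.9% | 53.8% |
| 10/90 cut | 34.2% | 37.4% |
| Tertiles, scored (1 df) | 79.3% | 70.4% |
| Tertiles, categories (2 df) | – | 60.1% |

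The 25% and 10% shares are assumptions, because the documents do not give the share beyond any fixed cut. The shape of the covariate also matters: a median split of a uniform covariate loses 25%, and of right-skewed ones 41% to 52%.

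**3. Cost at this trial's size.** The standard error of the interaction log hazard ratio per SD is about 2/√events. Primary events are 1,900 × 0.11 = 209 with complete follow-up, or about 190 allowing for the SAP's follow-up pattern and losses. The test level is assumed to be two-sided 0.05, the SAP 3.4 level for unpowered secondary endpoints; SAP 3.5 states none, and the 0.15 in SAP 3.9.2 is for region only.

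| Hazard-ratio ratio per SD | Continuous (190 to 209 events) | Median split | Cost, points |
|---|---|---|---|
| 1.1 | 10–11% | 8–9% | 2 |
| 1.2 | 24–26% | 17–18% | 7–8 |
| 1.3 | 44–48% | 30–33% | 14–15 |
| 1.4 | 64–68% | 46–49% | 18–19 |
| 1.5 | 80–83% | 61–65% | 19 |
| 1.6 | 90–93% | 73–77% | 15–17 |

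Worked line for 1.5 and 190 events: ln 1.5 / (2/√190) = 0.405/0.145 = 2.79, so power is Φ(2.79 − 1.96) = 80%. For the split, 2.79 × √0.637 = 2.23, so power is Φ(0.27) = 61%.

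For the composite with revascularization (about 380 to 418 events) the cost is 4 points at 1.1, 13–14 at 1.2, 19 at 1.3 and 3–4 at 1.6.

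**4. Simulation check.** Cox models were run with N = 1,900, 11% at 3 years, 29 months' accrual, 2 years' minimum follow-up and 8% loss, 1,500 runs each. At 1.49 per SD the continuous test had 77.3% power and the median split 57.5%. At 1.2 the figures were 24.7% and 16.1%.

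**5. The reverse case.** If the true effect is a step at the median, the fractions swap: when the split has 80% power, the linear term has 61%.

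**The case against.** The strongest reply is that SAP 3.5 claims nothing these tests could fail to deliver. It calls the comparisons descriptive. Protocol 5.3 says the trial is underpowered in any subgroup, and SAP 3.4.4 and 3.10 warn about reading such p-values. This stands: no power statement, alpha allocation or success criterion depends on these tests. It does not remove the case for using data already held, because the SAP still runs a test and ties a display to its significance.

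The cuts are also not arbitrary. SYNTAX 23 is a randomization stratum (Protocol 7.2.12, SAP 2.8), and 33 is the eligibility limit (Protocol 6.5.3). Protocol 7.3.6 uses a creatinine clearance of 60 ml/min as a renal threshold. Protocol Tables 2-1 and 2-2 contrast scores of 33 or more with 0 to 32, which fits a threshold at least as well as a gradient. This is a good reason to keep the cuts and to check linearity. It is not a reason to have no continuous test.

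That the cuts enter the model is an inference. SAP 3.5 refers to table mockups not available here, and SAP 3.6.1.4 separately plans work on the utility of the scores. The inference is strong, given the display by subgroup and the explicit categorising of ACEF, but it is not a stated rule.

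Finally, for weak interactions the continuous test is underpowered too, so the change would not make a flat forest plot proof of consistency. That also stands.

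**Conclusion.** The point holds as a cheap improvement to an exploratory analysis. All eight scores appear only in categorised form, and no continuous interaction is specified. Under a roughly normal covariate and a linear interaction, a median split loses about 36% of the information and tertiles about 21%. The cost is about 19 points where the continuous test would have 80% power, and about 2 to 15 points for hazard-ratio ratios of 1.1 to 1.3 per SD on the primary endpoint.

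A reader might infer more than this supports:

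- That every listed test loses a third or more of the information. Tertiles do not, nor does a flat covariate split at its median.
- That the plan carries a fixed cost of about 18 points. For the primary endpoint a cost of that size arises near a ratio of 1.4 to 1.5 per SD; no passage establishes an interaction that large.
- That cuts are always inferior. A step at the cut reverses the ranking.
- That a trial conclusion is weakened. None rests on these tests.

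**What to change.** In SAP 3.5, pre-specify one interaction test per score for age, BMI, LVEF, creatinine clearance, core-lab SYNTAX, clinical SYNTAX, SYNTAX II and ACEF. Enter the covariate as continuous, linear per SD, and use a restricted cubic spline to check for non-linearity. Name this as the main interaction p-value for that score, and label it in the forest plot as coming from the continuous model, since it does not test the strata printed beside it. State the significance level.

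Keep all listed cuts, including the design-based SYNTAX cuts at 23 and 33, for Kaplan-Meier rates, differences and hazard ratios by subgroup. Keep the statement that these analyses are unpowered and descriptive.

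The cost is SAP wording, a few lines of code and some additional exploratory models across eight scores and three endpoints. No new data are needed. The main downside is the linearity assumption, which is least secure for bounded or skewed scores such as SYNTAX; the spline is there to expose that.

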3.6 EXPLORATORY ANALYSIS

3.6.1 Exploratory Composite Endpoint Analysis

3.6.1.1 Weighted Composite Endpoint

Exploratory analysis comparing PCI and CABG on the weighted composite endpoint of all cause death, MI or stroke (mRS \ge 1 and increase by \ge 1 from baseline) occurring up to 3 years post randomization will be performed. The weighting algorithm will be based on that developed for death, MI, and stroke by Tong et al.⁸.

The 3 year Kaplan Meier event rates will be calculated for columns 2 and 3 below as well as the difference between the two. The relative weights are from the Tong reference. The normalized relative weight is calculated as follows:

Normalized Relative Weight = (Relative Weight for event/Relative Weight Sum) x Number of different types of events

| Event | KM estimate in CABG by 3 years | KM estimate in PCI by 3 years | Difference (PCI- CABG) | Relative Weight from Tong et al | Normalized Relative Weight from Tong et al | Adjusted Difference |
|-----------|---|--|------------------------------|--|--|------------------------|
| Death | | | | 0.23 | 1.25 | |
| Stroke | | | | 0.18 | 0.98 | |
| MI | | | | 0.14 | 0.76 | |
| Composite | | | | 0.55 | | |

Adjusted Difference = Difference x Normalized Relative Weight

The adjusted difference will then be placed into the formula for the Z statistic in Section 2.3.1 and pvalues and 95% confidence intervals will be displayed from this.

3.6.1.2 The Win Ratio

Exploratory analysis of comparing PCI and CABG using the win ratio calculated by Pocock et al method⁸ with the the unmatched approach⁷ will be performed. The outcomes used in calculating the win ratio ordered by their clinical importance (from high to low) will be all-cause death (high), stroke (mRS \geq 1 and increase by \geq 1 from baseline) and MI (low). Here are the steps needed to follow for this calculation:

Let N_n = total patients on PCI

Let N_s= total patients on CABG

Compare the timing of death, stroke and MI for each patient on PCI to each patient on CABG ($N_n x N_s$ comparisons) for the shortest time duration that exists between each pair of patients.

Classify each patient into one of 7 categories:

- (a) PCI patient died prior to CABG patient
- (b) CABG patient died prior to PCI patient
- (c) PCI patient had stroke prior to CABG patient
- (d) CABG patient had stroke prior to PCI patient
- (e) PCI patient had MI prior to CABG patient
- (f) CABG patient had MI prior to PCI patient
- (g) None of the above

Since groups b, d and f are in favor of PCI, $N_b + N_d + N_f = N_{win}$

Since groups a, c and e are not in favor of PCI, $N_a + N_c + N_e = N_{loss}$

Win Ratio (R_w) = N_{win}/N_{loss}

A p-value will be calculated for the Finkelstein-Schoenfeld test ¹⁰, as well as a 95 % CI interval will be calculated using bootstrapping methods¹¹.

3.6.1.3 Covariate Adjusted Analysis

A multivariable Cox model (or logistic regression if the proportional hazards assumption is not met) will be performed, adjusting for baseline variables historically known to be prognostically important in order to identify independent correlates for the outcomes of interest, as follows (number of variables selected to avoid model over-fitting; i.e. ~1 variable for every 10 events based on the anticipated rates):

Outomce = All-cause death/MI/stroke up to 30 day:

• age, gender, diabetes, LVEF, SYNTAX score groups (core lab), randomization arm (forced in)

Outcome= All-cause death/MI/stroke up to 3-year:

• age, gender, diabetes, hypertension, hyperlipidemia, prior MI, current smoking, prior cerebrovascular disease, prior PAD, prior heart failure, prior COPD, presentation in ACS vs stable CAD, baseline anemia, baseline creatinine clearance, LVEF, SYNTAX score groups (core lab), randomization arm (forced in)

Outcome= All-cause death/MI/stroke/unplanned revascularization up to 3-year:

• same as all all-cause death/MI/stroke

Continuous data such as age will be entered as continuous except as otherwise noted.

For Syntax score groups: <23, 23-32, >32, two dummy variables will need to be created:

If Syntax score < 23 then Syntax23=1; Else if Syntax ne . then Syntax23 = 0; If Syntax score > 32 then Syntax32=1; Else if Syntax ne . then Syntax32 = 0; Add both of the above dummy variables to the model in place of the 3 way Syntax I score.

Appropriate methods may be used to impute missing baseline values.

1). Test the proportional hazard assumption:

The proportional hazard assumption will first be tested by plotting the log-negative-log survival curves vs the log of survival time for each level of treatment group against each covariate one at a time.

Code to Test Proportional Hazard Assumption: proc lifetest data=DATAXX plot=(lls) noprint; time Timevar*Eventvar(0); strata Covariate; run:

2). If it is determined that the proportional hazard assumption is NOT violated then a Cox regression model will be performed with a stepwise option.

Code for Cox model where Proportion Hazard Assumption is **Not** violated: Proc phreg data=infile; Model timevar*Eventvar(0)=group *baselinevars*; Run;

Summary tables from this model will include failure rates (Kaplan-Meier estimates), adjusted hazard ratios, confidence interval for the hazard ratio, and a p-value.

3). If it is determined that the proportional hazard assumption is violated then a Logistic regression model will be performed adjusting for time on study with a stepwise option.

Code for Logistic Regression used when Proportional Hazard Assumption is violated: proc logistic data= DATAXX descending; class Group;

model Event (event=1) =TimeVar Group baselinevars/ rl;

run;

- Where Event = all first events from randomization or procedure date to 1095 or 30 days (dependent on outcome)
 - Timevar = Days from Randomization or procedure date to last data point available for patient while on study. If the patient did not drop out prior to the analysis time point then this will be set to the analysis time point.

The odds ratio, 95% confidence interval of the odds ratio and p-value will be presented from this logistic model

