2.5.1 Primary Endpoint

The primary endpoint of all cause death, MI or stroke (mRS \geq 1 and increase by \geq 1 from baseline) occurring up to 3 years post randomization will be evaluated using the difference in Kaplan-Meier failure rates in the intent-to-treat population. For the primary endpoint, sample size calculations for the Com-Nougue approach¹, which utilizes the difference in Kaplan-Meier failure rate estimates, were derived using simulations. The Com-Nougue approach was very similar to that calculated using the asymptotic approach (difference \leq 0.5%). Therefore, the asymptotic test was used to approximate the power for the Com-Nougue approach using PASS 2008 (NCSS, LLC. Kaysville, Utah)³.

The hypothesis test is designed to show non-inferiority of PCI to CABG for the primary endpoint via the Z statistic, which is a normal approximation to the Binomial, with a one-sided alpha of 0.025. The null (H_0) and alternative (H_A) hypotheses are:

```
H0: F_{PCI-PE}(T) - F_{CABG-PE}(T) \ge \Delta_{PE}
```

```
HA: F_{PCI-PE}(T) - F_{CABG-PE}(T) < \Delta_{PE}.
```

 F_{PCI-PE} and $F_{CABG-PE}$ are the Kaplan-Meier estimates of failure rate of the primary endpoint at 3 years in the PCI and CABG arms, respectively. Δ_{PE} is the non-inferiority margin for the primary endpoint.

The sample size calculation is based on the following assumptions:

- primary endpoint event rate is 11% in each treatment arm at 3 years (using 3-year event rates from the SYNTAX trial, the most contemporary reference dataset)
- minimum time to follow-up is 2 years
- median time to follow-up is approximately 3 years
- 8% lost to follow-up at 3 years
- non-inferiority margin $\Delta_{\text{PE}} = 4.2\%$
- one-sided alpha = 0.025
- accrual time of 29 months.

A sample size of 1,900 subjects (950 per arm) will provide approximately 80% power to

demonstrate non-inferiority of PCI to CABG.

If non-inferiority is met, superiority testing will be performed with a one-sided alpha of 0.025. The null (H_0) and alternative (H_A) hypotheses for the superiority test are:

H₀: $F_{PCI-PE}(T) - F_{CABG-PE}(T) \ge 0$

H_A: $F_{PCI-PE}(T) - F_{CABG-PE}(T) < 0$.

Using a one-sided alpha of 0.025, assuming 8% lost to follow-up at 3 years, the trial will have approximately 80% power to demonstrate superiority with a difference of 3.84% of PCI to CABG (e.g. 7.16% in the PCI arm vs. 11% in the CABG arm).

2.5.2 Major Powered Secondary Endpoints:

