The first major powered secondary endpoint is defined as the composite of all cause death, MI, or stroke (mRS \geq 1 and increase by \geq 1 from baseline) occurring up to 30 days post randomization. It will be evaluated using the difference in Kaplan-Meier rates tested using the Com-Nougue approach¹ which is similar to the normal approximation to the binomial. The null (H₀) and alternative (H_A) hypotheses for non-inferiority of this major secondary endpoint is:

H₀: $F_{PCI-PE30}(T) - F_{CABG-PE30}(T) \ge \Delta_{PE30}$

H_A: $F_{PCI-PE30}(T) - F_{CABG-PE30}(T) < \Delta_{PE30.}$

 $F_{PCI-PE30}(T)$ - $F_{CABG-PE30}(T)$ is the difference in Kaplan-Meier rates at 30 days between PCI and CABG arms and Δ_{PE30} is the non-inferiority margin for this powered secondary endpoint.

The power calculation is based on the following assumptions:

- composite event rate is 3% in each treatment arm at 30 days
- non-inferiority margin $\Delta_{\text{PE30}} = 2\%$
- one-sided alpha = 0.05

A sample size of 1,900 subjects (950 per arm) will provide approximately 80% power to demonstrate non-inferiority of PCI to CABG.

The second major powered secondary endpoint is defined as the composite of all cause death, MI, stroke, or unplanned revascularization for ischemia occurring by 3 years post randomization. This composite will be evaluated using the difference in Kaplan-Meier failure rates at 3 years between CABG and PCI in all 3 patient populations. The hypothesis is designed to show non-inferiority of PCI to CABG with a one-sided alpha of 0.05. The null (H₀) and alternative (H_A) hypotheses for non-inferiority of this powered secondary endpoint are:

H₀: $F_{COMP-PCI}(T) - F_{COMP-CABG}(T) \ge \Delta_{COMP}$ H_A: $F_{COMP-PCI}(T) - F_{COMP-CABG}(T) < \Delta_{COMP}$. $F_{COMP-PCI}(T) - F_{COMP-CABG}(T)$ is the difference in failure rates at 3 years between CABG and PCI and Δ_{COMP} is the non-inferiority margin for this powered secondary endpoint.

The power calculation is based on the following assumptions:

- composite event rate is 22% in each treatment arm at 3 years
- minimum time to follow-up is 2 years
- median time to follow-up is approximately 3 years
- 8% lost to follow-up at 3 years
- non-inferiority margin $\Delta_{\text{COMP}} = 8.4\%$
- one-sided alpha = 0.05
- accrual time of 29 months

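### The exploratory covariate-adjusted model calls for stepwise selection that the printed code lacks and that inflates the retained estimates; its proportional-hazards plot cannot be read for continuous covariates

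*SAP*

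**What the plan says.** SAP 3.6.1.3, within the exploratory analyses, plans a multivariable model for each of three outcomes. It uses baseline factors with an established prognostic role and aims to find independent correlates of outcome. The lists are capped: "number of variables selected to avoid model over-fitting; i.e. ~1 variable for every 10 events based on the anticipated rates". The 30-day list has 6 variables including arm. The two 3-year outcomes share a list of 17 including arm. Only the arm is marked as forced in.

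If proportional hazards is accepted, "a Cox regression model will be performed with a stepwise option". If not, a "Logistic regression model will be performed adjusting for time on study with a stepwise option". Neither sentence gives an entry or stay level. The printed PHREG and LOGISTIC statements list group and the baseline variables with no selection option.

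The choice between the two models rests on log-log survival plots made one covariate at a time, coded in PROC LIFETEST as "strata Covariate". The same section says: "Continuous data such as age will be entered as continuous except as otherwise noted". It gives categories for SYNTAX score but no cut-points for age, LVEF or creatinine clearance.

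**The concern.** There are two separate defects.

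**Selection.** Choosing known prognostic factors and capping their number by events is the usual preparation for fitting all of them. A stepwise pass afterwards keeps a covariate only when its estimate is large relative to its standard error. Reported hazard or odds ratios are therefore too far from 1 on average, and the usual intervals and p-values take no account of the selection. These are the results the model is meant to deliver. Text and code also lead to different models, so two programmers could each follow the section and report different results. Nothing keeps the two SYNTAX dummies together, so selection could retain one and change the reference group. Nor is the follow-up-time term in the logistic branch marked as forced in.

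**Proportional-hazards check.** With no cut-points, a numeric stratum variable gives one survival curve per distinct value. The plot decides whether a hazard ratio or an odds ratio is reported, and for continuous covariates it gives no usable information. The text also describes plots by treatment group, which the code does not produce.

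**Working it through.** **Inputs from the SAP.** Sample size (2.5.1): "A sample size of 1,900 subjects (950 per arm) will provide approximately 80% power to" show non-inferiority. Three-year death/MI/stroke (2.5.1): "primary endpoint event rate is 11% in each treatment arm at 3 years". Thirty-day composite (2.5.2): "composite event rate is 3% in each treatment arm at 30 days". Three-year composite with revascularization (2.5.2): 22%.

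**Step 1: the plan's own sizing rule.** Expected events are 1900 × 0.03 = 57, 1900 × 0.11 = 209 and 1900 × 0.22 = 418. SYNTAX group takes two dummies, so 6 variables are 7 parameters and 17 are 18.

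| Outcome | Events per variable | Events per parameter |
|---|---|---|
| 30 days | 57/6 = 9.5 | 57/7 = 8.1 |
| 3 years, death/MI/stroke | 209/17 = 12.3 | 209/18 = 11.6 |
| 3 years, with revascularization | 418/17 = 24.6 | 418/18 = 23.2 |

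The rule of about 10 reproduces for the full lists, so selection is not needed to satisfy it. The logistic branch adds a time term: 57/8 = 7.1 per parameter at 30 days. With staggered follow-up and 8% loss (exponential assumption), about 188 primary events would be observed by the analysis, or 188/17 = 11.1 per variable.

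**Step 2: inflation after selection.** The SAP gives no entry level, covariate effect or prevalence. I assume entry at 0.05 and a binary covariate, uncorrelated with the others, with prevalence p. Then SE = 1/√(D·p(1−p)) for D events, and z is normal with mean m = log(HR)/SE and variance 1. The mean z given |z| > 1.96 is m + [φ(1.96 − m) − φ(1.96 + m)]/P(|z| > 1.96). Dividing it by m gives the overstatement of the log HR.

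Example (D = 57, p = 0.5, HR 1.3): m = 0.2624 × √14.25 = 0.990. The conditional mean is 0.990 + (0.2492 − 0.0051)/0.168 = 2.44, and 2.44/0.990 = 2.5.

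| Events | HR 1.3 | HR 1.5 |
|---|---|---|
| 57 | 2.5 | 1.7 |
| 209 | 1.44 | 1.10 |
| 418 | 1.15 | 1.01 |

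At 25% prevalence and HR 1.3, the mean selected HR is 2.07 at 57 events and 1.53 at 209. On the log scale these are 0.728/0.262 = 2.8-fold and 0.425/0.262 = 1.6-fold.

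**Step 3: interval coverage for retained covariates (HR 1.3, same assumptions).** At 57 events, nominal 95% intervals cover the true value 84% of the time at 50% prevalence and 80% at 25%. At 209 events coverage is 95% and 93%. A small Cox stepwise simulation agrees: coverage for selected terms was 74% in a 30-day-like setting (60 runs) and 95% in a 3-year-like setting (only 12 runs). The full model gave 97% and 98%.

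**Step 4: the plot.** The numbers of distinct values are assumptions. About 50 ages give 209/50 = 4.2 events per curve at 3 years and 57/50 = 1.1 at 30 days. About 45 LVEF values give 4.6 and 1.3. About 1000 creatinine-clearance values give 0.2 and 0.06. Curves this sparse cannot be compared for parallelism.

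**The case against.** The section can be read as coherent: a capped list of candidates, followed by selection. Marking the arm as forced in makes sense only if the other terms can be dropped. The code uses placeholder names, so the missing option may be shorthand. That reading is fair, but it still leaves the entry and stay levels unstated and the code producing a different model.

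The inflation depends on assumed effects and prevalence, and it fades for strong factors and many events. This stands. A reader might infer that the adjusted results are unreliable throughout. The calculations do not support that for the 3-year models, where coverage stays near nominal and a factor with HR 1.5 is overstated by 10% or less on the log scale at 50% prevalence.

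A reader might also blame the stepwise step for noise variables appearing significant and for real but modest factors being missed. A full model read at 0.05 has both problems to the same degree, so neither is evidence against selection here.

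Finally, SAP 3.5 has cut-points for age, LVEF and creatinine clearance that could serve the plots, and most listed covariates are categorical and plot normally. This narrows the second defect to three covariates. Section 3.6.1.3 does not refer to those cut-points.

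**Conclusion.** The point holds as a minor one. The text asks for an unspecified stepwise procedure that the printed code does not run and that the plan's own sizing rule makes unnecessary. Its demonstrable harm is overstatement of retained effects. This is substantial at 30 days (about 1.7- to 2.5-fold on the log scale for HR 1.5 to 1.3) and mild to moderate at 3 years (1.01- to 1.44-fold), assuming entry at 0.05 and 50% prevalence. The calculation is for the Cox branch; the same mechanism applies to the logistic branch. For age, LVEF and creatinine clearance, the plot that chooses between the branches is uninformative as coded.

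It would be wrong to infer any threat to the trial's main conclusions. The primary and powered secondary tests are unadjusted differences in Kaplan-Meier rates. The arm is randomized and forced into the adjusted model. SAP 3.10 already treats p-values outside the primary and powered endpoints as hypothesis-generating.

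**What to change.** - Delete the stepwise wording in both the Cox and the logistic paragraphs, and fit the full listed set with arm, as the printed code does. If selection is kept, state entry and stay levels, keep the SYNTAX dummies together, force in the time term, make the code match, and label the estimates as selected.
- For age, LVEF and creatinine clearance, replace the stratified plot with scaled Schoenfeld or cumulative residuals (`ASSESS PH / RESAMPLE` in PHREG) or a covariate × log(time) term. Keep log-log plots for arm and categorical covariates.

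The cost is two text edits and a line or so of code, with no change to data, sample size or any confirmatory test. There is one small downside: per parameter, the 30-day full model falls slightly below the SAP's rule (8.1, or 7.1 in the logistic branch), although it is close to it per variable (9.5).
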